8.8.6 Stratified analyses, subgroup analyses and sensitivity analyses

All analyses will be stratified separately by vaccine brand (Comirnaty and Spikevax), and age at index date (i.e. age <65 years, ≥65 years).

Subgroup analyses will be conducted among people with immunocompromised status, recorded within 365 days prior to index date.

No sensitivity analyses are planned (Table 8.8.6.1).

Table 8.8.6.1 Sensitivity analyses – rationale, strengths and limitations

	What is being varied? How?	Why? (What do you expect to learn?)	Strengths of the sensitivity analysis compared to the primary	Limitations of the sensitivity analysis compared to the primary

	Phase II C3-002 – Study Protocol	
	Author(s): [name], [name], [name]	Version: v2.1
		Dissemination level: Public

8.9 Evidence synthesis

We will report analyses separately for each database and outcome. Additionally, we will pool the effect estimates across databases using random effect meta-analyses, I^2 for heterogeneity will be reported. Forest plots will be used to show results from meta-analyses. DATA MANAGEMENT

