Country	Name of Database	Justification for Inclusion	Health Care setting	Type of Data (EHR, claims, registries)	Number of active subjects	Feasibility count of outcome/exposure (if relevant)	Data lock for the last update	Contributing to objectives
United Kingdom	CPRD GOLD	Complete records on SARS-CoV-2 infection, Covid-19 vaccination, and outcome events of interest (excl. hospitalization for COVID-19)	Primary care	EHR	3M	Covid-19: 360,198 Comirnaty: 2,822,947 Spikevax: 311,069	01/2023	1-2 for outcome “COVID-19 related death” only, 4-6
The Netherlands	IPCI	Complete records on SARS-CoV-2 infection, Covid-19 vaccination, and outcome events of interest	Primary care	EHR	1.39M	Covid-19: 941,329 Comirnaty: 1,173,104 Spikevax: 463,315	12/2022	1-6
Spain	SIDIAP	Complete records on SARS-CoV-2 infection, Covid-19 vaccination, and outcome events of interest; Include inpatient admission information.	Primary care + linkage to hospital data	EHR	5.8M	Covid-19: 3,865,976 Comirnaty: 6,548,545 Spikevax: 3,371,395	06/2022	1-6

	Phase II C3-002 – Study Protocol	
	Author(s): [name], [name], [name]	Version: v2
		Dissemination level: Public

Clinical Practice Research Datalink GOLD, United Kingdom (University of Oxford)

The Clinical Practice Research Datalink (CPRD) is a governmental, not-for-profit research service, jointly funded by the National Institute for Health and Care Research and the Medicines and Healthcare products Regulatory Agency, a part of the Department of Health, United Kingdom (UK) (<https://cprd.com>). CPRD GOLD¹¹ comprises computerized records of all clinical and referral events in primary care in addition to comprehensive demographic information and medication prescription data in a sample of UK patients (predominantly from Scotland (52% of practices) and Wales (28% of practices). The prescription records include information on the type of product, date of prescription, strength, dosage, quantity, and route of administration. Data from contributing practices are collected and processed into research databases. Quality checks on patient and practice level are applied during the initial processing. Data are available for 20 million patients, including 3.2 million currently registered patients. Approval for this study was granted via the Research Data Governance Process.

Integrated Primary Care Information Project (IPCI), The Netherlands (Erasmus)

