8.6.3. Other covariates, including confounders, effect modifiers and other variables (where relevant)

Demographics

Patients' age at index date and sex will be identified.

Geographic location

We will use geographic location, e.g. GP surgery or healthcare regions to account for local vaccination, infection and testing rates.

Predominant SARS-CoV-2 variant

Calendar time will be used as a proxy to define exposure to the predominant variant, including "Alpha and earlier variants", "Delta", "Omicron" and "XBB variant or later dominant" for databases with sufficient recent data. Time periods are specified in section 8.3 Study Period.

Health conditions pre-index date

Individuals' history of the comorbidities will be identified over three time periods prior to the index date, and will be used for summary characterisation and calculation of large-scale propensity scores:

- 1) 30 days prior to one day prior index date,
- 2) 365 days prior to one day prior index date,
- 3) all available days observed up to one day prior to index date.

A range of health conditions will be assessed using the time windows above. Among these, the following conditions will be identified for summary characterisation: anxiety, asthma, chronic obstructive pulmonary disease, chronic kidney disease, chronic liver disease, COVID-19, atrial fibrillation, cancer (excluding non-melanoma skin cancers), dementia, depressive disorder, diabetes, GERD, heart failure, hypertension, hypothyroidism, inflammatory bowel disease (crohn's disease or ulcerative colitis), myocardial infarction, venous thromboembolism, stroke, transient ischaemic attack (TIA), rheumatoid arthritis, osteoporosis, alcohol or drug substance misuse and obesity.

Medications pre-index date

Pre-existing medication use will be identified using 2 time windows, defined as 365 days to one day prior to index date, and 30 days to 1 day prior to index date, and will be used to provide summary characterisation for patients and calculation of large-scale propensity scores.

Immunocompromised status at the index date

People who are immunocompromised at the index data will be defined by the recording of certain conditions or certain conditions plus treatments prior to index date. People will be considered immunocompromised if they have *one or more* of the following conditions recorded within 365 days prior to index date:

	Phase II C3-002 – Study Protocol	
	Author(s): [name], [name], [name]	Version: v2.1

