8.8.5 Objectives 4-6: Vaccine effectiveness to prevent post-acute COVID-19 complications

Objectives 4-6 evaluate vaccine effectiveness to prevent post-acute COVID-19 complications, namely new onset diabetes and cardiovascular complications, and will be conducted in all 3 databases.

Similar to objective 3, we will compare people with 1st dose vaccination vs. 2nd dose vaccination [cohort 5 vs. 6], 2nd dose vaccination vs. 3rd dose vaccination [cohort 6 vs. 7] and 3rd dose vaccination vs. 4th dose vaccination [cohort 7 vs. 8].

Study population

The study populations will be derived similar to the inclusion process outlined for objectives 1-3 above, including sequential matching. Inclusion criteria will be applied as outline in section 8.8.4 for Objective 3.

For objectives 4 and 5, people with the respective outcomes of interest, i.e. diabetes recorded anytime before their index date will be excluded for the respective objective. For objective 6, an outcome-free washout window of 365days prior to index date will be implemented.

	Phase II C3-002 – Study Protocol	
	Author(s): [name], [name], [name]	Version: v2.1
		Dissemination level: Public

We will require at least 12 months of follow-up after SARS-CoV-2 infection to assess post-acute complications for outcomes 5, 6, and 7. If people die within 12 months after COVID-19 they will contribute patient-time until death to the analyses. Only infections recorded 12 months before the end of data availability will be included.

Outcomes

- SARS-CoV-2 infection [for contextualization]
- SARS-CoV-2 infection + New onset diabetes Type 1 diabetes within 30-365 days after COVID-19
- SARS-CoV-2 infection + New onset diabetes Type 2 diabetes within 30-365 days after COVID-19
- SARS-CoV-2 infection + cardiovascular events (cerebrovascular disorders, dysrhythmias, ischemic and non-ischemic heart disease, pericarditis, myocarditis, heart failure and thromboembolic disease) in the 12 months after a SARS-CoV-2 infection

Vaccine effectiveness analyses for post-acute COVID-19 complications:

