
11. LIMITATIONS OF THE RESEARCH METHODS

General limitations:

- The study will be informed by routinely collected health care data and so data quality issues must be considered.
- We will use large-scale propensity scores to minimize measured confounding, and NCOs to assess potential residual confounding. However, given the observational nature of our data, we cannot rule out remaining confounding, which could partially account for findings in this study.

Study-specific limitations:

- Mandatory PCR test for people who tested positive in lateral flow home tests were skipped in early 2022. As not all positive home tests were reported and recorded as clinical diagnoses in primary care databases, it is likely that non-severe SARS-CoV-2 infections are underreported after 02/2022. Moreover, underreporting of COVID-19 for asymptomatic case is to be expected. Underreporting of COVID-19 could lead to misclassification of outcomes for Objectives 4-6, namely post-acute COVID-19 complications (diabetes, cardiac events). For objectives 4-6, we require a minimum follow-up time of 12months after SARS-CoV-2 to identify cases of new-onset diabetes and/or cardiovascular complications. With this, only infections recorded before 02/2022 will be included in the study.
- Routine screening has been impacted by the pandemic, and therefore diagnoses of new conditions, e.g. T2DM might have been delayed depending on testing practices.
- COVID-19 related hospitalization is unlikely to be underreported as people are likely to be asked about previous SARS-CoV-2 infections at hospital admission (Objective 3). However, positive COVID-19 test results that occur around hospitalization do not constitute a hospitalization *due to* COVID-19.

	Phase II C3-002 – Study Protocol	
	Author(s): [name], [name], [name]	Version: v2.1
		Dissemination level: Public

We will use the data cuts currently onboarded for DARWIN EU for CPRD, IPCI and SIDIAP. However, none of those is currently covering the period of XBB variant predominance. We therefore designed the study to assess objectives 1 and 2 to start at the time the 4th vaccine doses were made available for people.

MANAGEMENT AND REPORTING OF ADVERSE EVENTS/ADVERSE REACTIONS

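### For objectives 4-6 the 12-month infection rule leaves the three databases with different variant eras (SIDIAP Alpha only), and 8.9 pools them without using the variant-period variable already defined

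*Protocol*

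**What the plan says.** Section 8.8.5 runs objectives 4-6 (new-onset type 1 and type 2 diabetes, cardiovascular events) in all three databases, with follow-up from vaccination. It limits the infections that can lead to an outcome: "Only infections recorded 12 months before the end of data availability will be included".

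Section 11 fixes the data: "We will use the data cuts currently onboarded for DARWIN EU for CPRD, IPCI and SIDIAP". Table 8.2.1 gives the locks: CPRD GOLD "Spikevax: 311,069 01/2023", IPCI "Spikevax: 463,315 12/2022", and 06/2022 in the SIDIAP row. Section 11 also gives one consequence of the 12-month rule for the whole study, namely that only infections before 02/2022 are included.

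Section 8.6.3 defines a variant variable: "Calendar time will be used as a proxy to define exposure to the predominant variant". Table 7 lists it for all cohorts. Section 8.8.5 does not use it. Section 8.8.6 says "All analyses will be stratified separately by vaccine brand (Comirnaty and Spikevax), and age at index date", adds an immunocompromised subgroup and plans no sensitivity analyses. Section 8.9 reports each database separately and adds that "we will pool the effect estimates across databases using random effect meta-analyses", with I² and forest plots.

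**The concern.** The locks differ by up to seven months, and in 2021 seven months is the distance between one variant era and the next. Once the 12-month rule is applied, the databases no longer observe the same epidemic. One contributes a single era and the other two contribute mixtures.

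If an extra dose protects to a different degree against different variants, three databases with identical underlying effects would return three different hazard ratios. I² would then register era differences that look like differences between countries or data sources. The pooled any-variant vaccine effectiveness would be a blend whose proportions come from data-lock dates. With three databases, and era tied so closely to database, the two cannot be separated after pooling. The single cut-off in section 11 also hides the fact that SIDIAP stops much earlier.

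**Working it through.** **1. Reproduce the stated cut-off.** Cut-off = data lock minus 12 months.
- CPRD: 01/2023 gives 01/2022, which matches section 11's limit of before 02/2022.
- IPCI: 12/2022 gives 12/2021.
- SIDIAP: 06/2022 gives 06/2021.

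The stated figure is therefore right as the study-wide maximum, but it is CPRD's date only.

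**2. Split each eligible window by Table 8.3.1.** The window starts on 01/01/2021 (section 8.3). Delta starts on 01/06/2021 in the UK and 01/07/2021 in the Netherlands and Spain; Omicron starts on 15/12/2021 in all three. Changeover days count in the later period. The lock gives only a month, so each range runs from a lock at the start to a lock at the end of that month.

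| Database | Window (days) | Alpha | Delta | Omicron | Delta + Omicron |
|---|---|---|---|---|---|
| SIDIAP | 151 to 181 | 151 to 181 | 0 | 0 | 0% |
| IPCI | 334 to 365 | 181 | 153 to 167 | 0 to 17 | 153/334 = 45.8% to 184/365 = 50.4% |
| CPRD | 365 to 396 | 151 | 197 | 17 to 48 | 214/365 = 58.6% to 245/396 = 61.9% |

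SIDIAP is Alpha-only at either end of its lock month, because Delta starts in Spain the day after the latest possible cut-off.

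**3. By comparison.**
- *1 versus 2 doses:* the table above applies approximately.
- *2 versus 3 doses:* the earliest possible third dose is first approval (marketing approval table in 8.6.1) + 21 + 90 days. UK: 08/12/2020 + 111 days = 29/03/2021. EU: 21/12/2020 + 111 days = 11/04/2021. From those dates Delta and Omicron take 153/234 = 65% to 184/265 = 69% of IPCI's days and 214/278 = 77% to 245/309 = 79% of CPRD's. SIDIAP has only 51 to 81 days, all Alpha.
- *3 versus 4 doses:* the Abstract starts the fourth-dose period on 01/08/2022, after every infection cut-off in step 1. On that date there is nothing to pool.

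**4. Illustration of size (assumed values, not from the protocol).** Let the true hazard ratio (HR) be the same in all databases within an era, and mix on the log scale with later-era weights of 0 (SIDIAP), 0.5 (IPCI) and 0.6 (CPRD). Take variance of log HR = 4/events and add no sampling noise.

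With HR 0.4 in Alpha and 0.8 later:
- SIDIAP 0.40; IPCI 0.4^0.5 × 0.8^0.5 = 0.57; CPRD 0.4^0.4 × 0.8^0.6 = 0.61. Effectiveness is 60%, 43% and 39%.
- 100 events in each database: pooled HR 0.52, I² 19%.
- 400 events in SIDIAP and 100 in each of the others: pooled HR 0.49, I² 59%.

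With HR 0.4 and 0.6, the database values are 0.40, 0.49 and 0.51, the pooled HR is 0.46 or 0.43 for the same two event patterns, and I² is 0%. I² need not flag the mixture. With HR 0.6 in both eras, every value is 0.60 and there is no distortion.

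**The case against.** The any-variant definition of cohorts 5-8 is deliberate, and no objective asks for variant-specific effectiveness. Section 8.9 puts the database results first, and the pooled estimate is an addition under a random-effects model. All of this stands and softens the point. It does not remove it: a random-effects model allows for heterogeneity without saying where it comes from, and no stated output shows each database's infection window. Nor is this silence that an analysis plan would simply fill, since 8.8.6 fixes the strata and rules out sensitivity analyses.

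A reader might also infer more than the protocol supports:
- *That each database's HR is confounded by era.* Weekly sequential matching gives both members of a pair the same index date, and pairs are censored together. The trouble is what the pooled figure means.
- *That half or more of IPCI's and CPRD's eligible infections are Delta or Omicron.* The shares are calendar days. Infection counts by period are not given, and censoring at the next dose would shift the mix.
- *That SIDIAP dominates the pooled result because of its size.* Its feasibility entry, "Covid-19: 3,865,976 Comirnaty: 6,548,545 Spikevax: 3,371,395", has no stated period and is not a count of outcome events in matched pairs. Its weight is unknown, and its window is the shortest.
- *That all dose comparisons are equally affected.* For 2 versus 3 doses SIDIAP may add very little, and for 3 versus 4 there is nothing to pool on the stated dates.

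**Conclusion.** The concern holds as a limited point about interpretation. It follows from the protocol's own dates that SIDIAP's eligible window for objectives 4-6 is Alpha only, while later variants fill 46-50% of IPCI's and 59-62% of CPRD's eligible days. No planned analysis uses the variant variable, so the pooled any-variant effectiveness and I² would mix era with database wherever dose effectiveness differs by variant. Whether it differs, and by how much, cannot be settled from the protocol. The illustrative spread from 60% to 39% rests on assumed hazard ratios and on calendar time standing in for infections, and it falls to zero if effectiveness is constant across eras. The practical weight lies on the 1-versus-2-dose comparison. It is worth correcting because the remedy is cheap and the variable already exists.

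**What to change.** - **8.8.5 and section 11:** replace the single cut-off with each database's eligible infection window, and print those windows on the forest plots.
- **8.8.6:** add hazard ratios by variant period for objectives 4-6. Classify each event by the date of the qualifying SARS-CoV-2 infection, and split person-time at risk of infection at the Table 8.3.1 dates. Splitting by the date of the complication would misplace events: diabetes up to 365 days after a May 2021 infection could fall in the Omicron period. Merge Omicron with Delta where counts are too small, which is likely in IPCI with 0 to 17 Omicron days and suppression of cells below 5.
- **8.9:** pool across databases within the same period and comparison, at least over the common Alpha window, and report this beside the all-period pooled hazard ratio.

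Cost: some wording and one further split of data already in hand. The period-specific intervals will be wider, and the post-Alpha pool will hold only IPCI and CPRD.

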9. DATA MANAGEMENT

All databases have previously mapped their data to the OMOP common data model. This enables the use of standardised analytics and using DARWIN EU tools across the network since the structure of the data and the terminology system is harmonised. The OMOP CDM was developed and maintained by the Observational Health Data Sciences and Informatics (OHDSI) initiative and is described in detail on the wiki page of the CDM: <https://ohdsi.github.io/CommonDataModel> and in The Book of OHDSI: <http://book.ohdsi.org>

The analytic code for this study will be written in R, and will use standardized analytics wherever possible. Each data partner will execute the study code against their database containing patient-level data, and then return the results (csv files) which will only contain aggregated data. The results from each of the contributing data sites will then be combined in tables and figures for the study report.

9.1 Data storage and protection

For this study, participants from various EU member states will process personal data from individuals which is collected in national/regional electronic health record databases. Due to the sensitive nature of this personal medical data, it is important to be fully aware of ethical and regulatory aspects and to strive to take all reasonable measures to ensure compliance with ethical and regulatory issues on privacy.

All databases used in this study are already used for pharmaco-epidemiological research and have a well-developed mechanism to ensure that European and local regulations dealing with ethical use of the data and adequate privacy control are adhered to. In agreement with these regulations, rather than combining person level data and performing only a central analysis, local analyses will be run, which generate non-identifiable aggregate summary results.

The output files are stored in the DARWIN Remote Research Environment. These output files do not contain any data that allow identification of subjects included in the study. The RRE implements further security measures in order to ensure a high level of stored data protection to comply with the local implementation of the General Data Protection Regulation (GDPR) (EU) 679/20161 in the various member states.

10. QUALITY CONTROL

General database quality control

A number of open-source quality control mechanisms for the OMOP CDM have been developed (see Chapter 15 of The Book of OHDSI <http://book.ohdsi.org/DataQuality.html>). In particular, data partners will have run the OHDSI Data Quality Dashboard tool (<https://github.com/OHDSI/DataQualityDashboard>). This tool provides numerous checks relating to the conformance, completeness and plausibility of the mapped data. Conformance focuses on checks that describe the compliance of the representation of data against internal or external formatting, relational, or computational definitions, completeness in the sense of data quality is solely focused on quantifying missingness, or the absence of data, while plausibility seeks to determine the believability or truthfulness of data values. Each of these categories has one or more subcategories and are

	Phase II C3-002 – Study Protocol	
	Author(s): [name], [name], [name]	Version: v2.1
		Dissemination level: Public

evaluated in two contexts: validation and verification. Validation relates to how well data align with external benchmarks with expectations derived from known true standards, while verification relates to how well data conform to local knowledge, metadata descriptions, and system assumptions.

Study specific quality control

Vaccine exposure status, COVID-19 clinical diagnoses, and SARS-CoV-2 tests will be identified from the data using established code-lists used in previous studies. Those lists have been updated for this study to include the latest codes i.e. for new vaccines.

When defining conditions for outcomes of interest, i.e. new onset Type 1 and Type 2 Diabetes Mellitus, a systematic search of possible codes for inclusion will be conducted using CodelistGenerator R package²⁸. This software allows the user to define a search strategy and using this will then query the vocabulary tables of the OMOP common data model so as to find potentially relevant codes. Clinicians will review the resulting code lists to exclude irrelevant codes, such as for persisting disease or complications. In addition, the CohortDiagnostics R package (<https://github.com/OHDSI/CohortDiagnostics>) will be run if needed to assess the use of different codes across the databases contributing to the study and identify any codes potentially omitted in error.

For cardiovascular outcomes, concept sets used in previous vaccine safety studies will be used.

11. LIMITATIONS OF THE RESEARCH METHODS

General limitations:

- The study will be informed by routinely collected health care data and so data quality issues must be considered.
- We will use large-scale propensity scores to minimize measured confounding, and NCOs to assess potential residual confounding. However, given the observational nature of our data, we cannot rule out remaining confounding, which could partially account for findings in this study.

Study-specific limitations:

- Mandatory PCR test for people who tested positive in lateral flow home tests were skipped in early 2022. As not all positive home tests were reported and recorded as clinical diagnoses in primary care databases, it is likely that non-severe SARS-CoV-2 infections are underreported after 02/2022. Moreover, underreporting of COVID-19 for asymptomatic case is to be expected. Underreporting of COVID-19 could lead to misclassification of outcomes for Objectives 4-6, namely post-acute COVID-19 complications (diabetes, cardiac events). For objectives 4-6, we require a minimum follow-up time of 12months after SARS-CoV-2 to identify cases of new-onset diabetes and/or cardiovascular complications. With this, only infections recorded before 02/2022 will be included in the study.
- Routine screening has been impacted by the pandemic, and therefore diagnoses of new conditions, e.g. T2DM might have been delayed depending on testing practices.
- COVID-19 related hospitalization is unlikely to be underreported as people are likely to be asked about previous SARS-CoV-2 infections at hospital admission (Objective 3). However, positive COVID-19 test results that occur around hospitalization do not constitute a hospitalization *due to* COVID-19.

	Phase II C3-002 – Study Protocol	
	Author(s): [name], [name], [name]	Version: v2.1
		Dissemination level: Public

We will use the data cuts currently onboarded for DARWIN EU for CPRD, IPCI and SIDIAP. However, none of those is currently covering the period of XBB variant predominance. We therefore designed the study to assess objectives 1 and 2 to start at the time the 4th vaccine doses were made available for people.

MANAGEMENT AND REPORTING OF ADVERSE EVENTS/ADVERSE REACTIONS

Adverse events/adverse reactions were not collected or analyzed as part of this evaluation. The nature of this non-interventional evaluation, through the use of secondary data, does not fulfill the criteria for reporting adverse events, according to module VI, VI.C.1.2.1.2 of the Good Pharmacovigilance Practices (https://www.ema.europa.eu/en/documents/regulatory-procedural-guideline/guideline-good-pharmacovigilance-practices-gvp-module-vi-collection-management-submission-reports_en.pdf)

Only in the case of prospective data collection, there is a need to describe the procedures for the collection, management and reporting of individual cases of adverse events/adverse reactions.

